### Data Management

Several electronic resources will be used for data collection and management. Research Electronic Data Capture (REDCap) will be used to manage participant recruitment, scheduling, and tracking. All surveys will be collected via Computer-assisted Personal Interviews in which an interviewer reads the questions and enters the data into REDCap, programmed with variable range checks and skip rules. Fitabase®.com will track data synced from participants' Fitbit devices. Fitabase® is a secure research platform that collects and stores data from devices that connect to the internet. In addition to current data from users, a dashboard will show which devices have been recently synced, as well as individual device battery levels. The BrainHQ program tracks participant level and number of minutes spent in each activity. Data from BrainHQ, Fitabase®, and the accelerometers will be exported (using study ID variables) to SAS for merging and management.

All variables will be checked for errant values. Descriptive statistics will be computed for all items and scale scores. Distributions will be examined for non-normality and outliers. We expect outcome measures to be normally distributed. Data will be examined to determine normality and transformed if necessary. Outcome measures that cannot be transformed to achieve normality will be analyzed by appropriate generalized linear models available in SAS. All statistical tests will use  $\alpha = .05$ .

### Statistical Analyses

Under the direction of [name], all analyses will use an intent-to-treat approach (i.e., participants analyzed according to their assigned cell; **Figure 3**) independent of their actual dose of each intervention. All analyses will employ multi-level mixed models with repeated observations (baseline, 24, 48, and 72 weeks) nested within participants, and participants nested within cohorts. Three parameters for factorial design will be included in the models: (1) *Move* main effect, (2) *Mind* main effect, and (3) *Move* x *Mind* interaction effect. Time and interactions of time with the factorial design parameters will be included in the models. Potential covariates in the multi-level mixed models are in Table 5. Although many of these covariates may relate to memory level, they are generally less likely to influence change over time. Covariates will be at Level 2 (person level) or Level 1 (assessment level) as appropriate. To minimize the number of covariates in the final models, we will first test each candidate covariate individually in models for each memory outcome change over time (time x covariate interaction). We will retain only significant covariates in the final models.

Time can be handled flexibly with multilevel mixed models, allowing us to model hypothesized patterns of change over time that deviate from linear or quadratic patterns. For example, we expect that *Mind* effects will be greatest from baseline to 24 weeks, followed by a change plateau; thus, a parameterization of time would reflect a relatively large increase from baseline to 24 weeks followed by stabilization after 24 weeks. Adding a term for this discontinuity in memory level (coded 0, 1, 1, 1 for baseline, 24, 48, and 72 weeks, respectively) allows us to test this pattern. In contrast, for the *Move* effects, we expect a more gradual linear change in memory from baseline through 48-72 weeks; therefore, a discontinuity term may not be needed. The general multilevel mixed model for the proposed analyses can be represented by the following equations:

#### Observation-Level Model

$$Y_{ijk} = \pi_{0jk} + \pi_{1jk}(\text{time}) + \pi_{Pjk}(\text{time-varying covariates}) + \varepsilon_{ijk}$$

Where

$Y_{ijk}$  is the outcome measure at time  $i$  for person  $j$  in cluster  $k$ ;

$\pi_{0jk}$  is the intercept for person  $j$  in cluster  $k$ ;

$\pi_{1jk}$  is the level-1 coefficient for the time (change) effect for person  $j$  in cluster  $k$ ;

$\pi_{Pjk}$  are the level-1 coefficients for time-varying covariates (as needed) for person  $j$  in cluster  $k$ ; and  $\varepsilon_{ijk}$  is the random error term.

#### Person-Level Model

$$\pi_{0,jk} = \beta_{00k} + \beta_{01k}(\text{age}) + \beta_{02k}(\text{race}) + \beta_{03k}(\text{education}) + \beta_{04k}(\text{BMI}) + r_{0jk}$$

$$\pi_{1,jk} = \beta_{10k} + \beta_{11k}(\text{age}) + \beta_{12k}(\text{race}) + \beta_{13k}(\text{education}) + \beta_{14k}(\text{BMI}) + r_{1jk}$$

$$\pi_{P,jk} = \beta_{P0k}$$

Where

$\beta_{00k}$  is the outcome measure for cluster  $k$ ;

$\beta_{01k}$  through  $\beta_{04k}$  are the coefficients for person-level effects on the intercept;

$\beta_{11k}$  through  $\beta_{14k}$  are the coefficients for person-level effects on the time slope;

$\beta_{P0k}$  are the person-level means for the time-varying covariates;

$r_{0jk}$  is the person-level random effect for the intercept; and

$r_{1jk}$  is the person-level random effect for the time slope.

#### Cluster-Level Model

$$\beta_{00k} = \gamma_{000} + \gamma_{001}(\text{Move}) + \gamma_{002}(\text{Mind}) + \gamma_{003}(\text{MindMoves}) + \gamma_{004}(\text{ClinicSite}) + u_{00k}$$

$$\beta_{01k} = \gamma_{010}$$

⋮

$$\beta_{04k} = \gamma_{040}$$

$$\beta_{10k} = \gamma_{100} + \gamma_{101}(\text{Move}) + \gamma_{102}(\text{Mind}) + \gamma_{103}(\text{MindMoves}) + \gamma_{104}(\text{ClinicSite}) + u_{10k}$$

$$\beta_{11k} = \gamma_{110}$$

⋮

$$\beta_{14k} = \gamma_{140}$$

$$\beta_{P0k} = \gamma_{P00}$$

Where

$\gamma_{000}$  is grand mean (intercept) for the outcome measure;

$\gamma_{001}$  through  $\gamma_{003}$  are the intervention main effects and interaction effect on the mean for the outcome measure;

$\gamma_{004}$  is the Clinic Site effect on the mean for the outcome measure;

$\gamma_{010}$  through  $\gamma_{040}$  are the overall effects for the person-level covariates;

$\gamma_{100}$  is grand mean change over time on the outcome measure;

$\gamma_{101}$  through  $\gamma_{103}$  are the intervention main effects and interaction effect on change over time for the outcome measure;

$\gamma_{104}$  is the Clinic Site effect on change over time for the outcome measure;

$\gamma_{110}$  through  $\gamma_{140}$  are the overall effects for the person-level covariates on change over time of the outcome measure;

$u_{0jk}$  is the cluster-level random effect for the intercept; and

$u_{1jk}$  is the cluster-level random effect for the time slope.

It is expected that the person-level random effects for the intercept ( $r_{0jk}$ ) and time slope ( $r_{1jk}$ ) will be significant (i.e., there will be significant between-person variation in level of the outcome and rate of change over time). Although we will include them in the initial models, it is likely that the cluster-level random effects for the intercept ( $u_{0jk}$ ) and time slope ( $u_{1jk}$ ) will be non-significant. If non-significant, those random effects will be removed from the models. The time-varying covariates include time of day for the assessment (i.e., for models with BDNF as the dependent variable – see Aim 2 below) and discontinuities (see above).

**Aim 1 (primary): To determine the independent and combined efficacy of Move and Mind interventions on memory performance among women  $\geq 65$  years with CVD. Hypotheses: Move and Mind each will improve performance-based memory (main effects). In addition, there will be an interactive effect such that MindMoves will provide greater memory benefit than the sum of the main effects of Move and Mind.**

Aim 1 tests the main effects of the individual interventions (i.e., Move and Mind) as well as the interaction between the interventions. Outcome measures will be collected at baseline and 24, 48, and 72 weeks post-baseline. Because we hypothesize intervention effects on memory outcomes over time, significant Move x Time, Mind x Time, and Move x Mind x Time effects will provide evidence of significant main effects and a

significant interaction effect, respectively (parameters  $\gamma_{101}$ ,  $\gamma_{101}$ , and  $\gamma_{103}$  above).

Measures for Aim 1 (see section 4.3):

Primary Measures for Aim 1:

- [1] East Boston Memory Test (episodic memory)
- [2] Category Fluency (semantic memory)
- [3] Digit Span Forwards and Backwards (working memory)

Secondary Measures for Aim 1:

- [4] NIH Toolbox® Fluid Cognition Index (episodic memory, working memory, executive function, processing speed)

***Aim 2 (secondary): To determine the independent and combined efficacy of the *Move* and *Mind* interventions on memory-related serum biomarkers (brain-derived neurotrophic factor [BDNF], vascular endothelial growth factor [VEGF], insulin-like growth factor 1 [IGF-1]) among women  $\geq 65$  years with CVD. Hypotheses: *Move* and *Mind* each will improve serum biomarkers (main effects). In addition, there will be an interactive effect such that *MindMoves* will show a greater increase in biomarkers than the sum of the main effects of *Move* and *Mind*.***

Aim 2 tests the effects of *Move* and *Mind* individually (main effects) and combined (interaction effect) on memory-related serum biomarkers (BDNF, VEGF, IGF-1) at 24, 48, and 72 weeks post-baseline. Analyses will use multi-level mixed models as described in Aim 1. Due to known variation in BDNF levels throughout the day, time of day of assessment will be included as a time-varying covariate for analyses of impact on BDNF.

Some secondary analyses related to Aims 1 and 2 are planned. We will test intervention effects on the target behaviors of physical activity (Actigraph accelerometer, self-report) and cognitive activity (self-report). Although both *Move* and *Mind* have proven efficacy, we will verify their impact on target behaviors. Second, we will explore whether there is evidence that the treatment effects of *Mind* and/or *Move* were attenuated by behavior changes among those who did not receive one or both intervention (e.g., due to increased use/ownership of physical activity monitors and/or computers). For those in the control group, we expect no change in target behaviors (physical activity for *Move*, cognitive activity for *Mind*). From the models in the former secondary analysis described above, we will calculate estimates of the time slope for the appropriate no-treatment groups and confirm that they are not significantly greater than zero. We also will assess change in use/ownership of physical activity monitors and computers.

Measures for Aim 2 (see section 4.3):

- [5] BDNF
- [6] VEGF-A
- [7] IGF-1

***Aim 3 (exploratory): To examine depressive symptoms and genetic factors (APOE- $\epsilon 4$  allele, BDNF genotype) as potential moderators of the association between changes in target behaviors (physical activity, cognitive activity) and health outcomes (memory performance, serum biomarkers).***

Aim 3 examines depressive symptoms and genetic factors as potential moderators of intervention efficacy on memory performance and effect on memory-related serum biomarker levels. A continuous measure of baseline depressive symptomatology (CES-D) and dichotomous indicators of *BDNF* genotype and *APOE- $\epsilon 4$*  allele status will be added to the models in Aims 1 and 2. Intervention effect x time x moderator interaction effects will be evaluated for significant moderation of the intervention effects by these three variables. We expect that intervention effects will be attenuated by higher levels of depressive symptoms and by the presence of a *BDNF*Met genotype or *APOE- $\epsilon 4$*  allele. When significant moderation is found, we will test the extent to which moderation occurs between the intervention and uptake of the target behaviors (e.g., physical activity and cognitive activity) as well as between change in target behaviors and health outcomes (e.g., memory performance and memory-related serum biomarkers). For example, depressive symptoms are hypothesized to reduce the degree to which changes in physical activity and cognitive activity lead to improved memory. In addition, participants with higher levels of depressive symptoms may participate less in the intervention and therefore exhibit fewer changes in target behaviors. Though power is likely to be lower for Aim 3 than for Aims 1 and 2, these analyses will contribute important deductive data for planning future studies.

In terms of the multilevel model presented above, a person-level covariate ( $\beta_{15k}$ ) will be added to the time equation ( $\pi_{1jk}$ ). A corresponding cluster-level equation for  $\beta_{15k}$  also will be added to the equations. Parameters  $\gamma_{151}$ ,  $\gamma_{152}$ , and  $\gamma_{153}$  represent moderation of the *Move* main effect, *Mind* main effect and *MindMoves* interaction effect respectively.

$$\pi_{1jk} = \beta_{10k} + \beta_{11k}(\text{age}) + \beta_{12k}(\text{race}) + \beta_{13k}(\text{education}) + \beta_{14k}(\text{BMI}) + \beta_{15k}(\text{moderator}) + r_{1jk}$$
$$\beta_{15k} = \gamma_{150} + \gamma_{151}(\text{Move}) + \gamma_{152}(\text{Mind}) + \gamma_{153}(\text{MindMoves})$$

Measures for Aim 3 (see section 4.3):

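### Optional precision gain: the model leaves arm means free at baseline, although randomisation makes them equal in expectation; the planned arm-by-time tests remain valid in this respect

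*SAP*

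**What the plan says.** The SAP (Statistical Analyses) puts baseline in the outcome vector with weeks 24, 48 and 72, in a mixed model with participants nested in cohorts. Under Cluster-Level Model, the equation for the intercept `beta_00k` contains Move, Mind and MindMoves with free coefficients `gamma_001` to `gamma_003`, which "are the intervention main effects and interaction effect on the mean for the outcome measure". The slope equation carries the matching terms `gamma_101` to `gamma_103`. Aim 1 rests only on the interactions of time with Move, with Mind and with their product.

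Protocol C3 has each cohort of 10-11 women recruited and measured at baseline before it is randomised.

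On the shape of change, the SAP anticipates for Mind "a relatively large increase from baseline to 24 weeks followed by stabilization after 24 weeks", to be captured by a term coded 0,1,1,1. For Move, "we expect a more gradual linear change in memory from baseline through 48-72 weeks". The Cluster-Level Model lists discontinuities among the time-varying covariates and gives those covariates one coefficient common to all arms. No time origin is stated.

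On cohort effects, the SAP says "it is likely that the cluster-level random effects for the intercept" and for the slope will be non-significant, and then: "If non-significant, those random effects will be removed from the models".

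Aim 2 uses the same model.

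**The concern.** If time is 0 at baseline and the time effect has the right shape, `gamma_001` to `gamma_003` are arm differences before any intervention. Randomisation makes their expectation zero. The model spends information estimating three quantities whose value is known by design, and Aim 1 tests none of them.

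Precision is scarce here: there are 6 cohorts per cell, and an interaction is among the primary tests. A constrained longitudinal model keeps baseline as an outcome but places arm effects only in the time terms, so it could recover some precision from data already collected.

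A related gap concerns the Mind pattern. With the step printed only as a common covariate, no printed term carries a jump specific to Mind. A linear fit with free intercepts then moves part of such a jump into `gamma_002`, which Aim 1 does not test.

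**Working it through.** **Inputs.** From the SAP (Power Analysis): correlation r = 0.7, 24 cohorts, 254 recruited, 216 after 15% attrition, d = 0.30, 80% power. The SAP gives no ICC, slope variance or intercept-slope covariance, so these are assumed. Baseline variance is 1, split 0.7 between persons and 0.3 residual. Visits are t = 0,1,2,3. Person slope variance is tau, cohort intercept variance u0, cohort slope variance u1. There are 9 analysed women per cohort (216/24), and each contrast is half against half (12 v 12 cohorts, 108 v 108 women).

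**1. The SAP's own figure.** 254 x 0.85 = 215.9, i.e. 216. Two variance bases reach about 80%:
- Change score, 2(1-r) = 0.60, ICC 0: SE = sqrt(2 x 0.60/108) = 0.105; 0.30/0.105 = 2.85; power 81%.
- Baseline-adjusted, 1-r^2 = 0.51, ICC 0.02: design effect 1 + 8 x 0.02 = 1.16; variance 0.592; SE 0.105; ratio 2.87; power 82%.

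With 0.60 and ICC 0.02 power is 75%; with 0.51 and ICC 0 it is 87%. The SAP says clustering was allowed for but gives no ICC, so the basis used cannot be determined.

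**2. Only linear time interacts with arm (as printed).** Write a = 0.7 + 9u0 and b = tau + 9u1. Per-person variance of the slope contrast:
- Arm intercepts free: 0.3/5 + b = 0.06 + b.
- Arm intercepts set to zero: 0.3/[14 - 36a/(0.3 + 4a)] + b.

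With a = 0.7 the second is 0.3/5.871 + b = 0.0511 + b. Savings:

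| tau | u0 | u1 | Free | Constrained | Saving |
|---|---|---|---|---|---|
| 0 | 0 | 0 | 0.0600 | 0.0511 | 14.8% |
| 0.01 | 0 | 0 | 0.0700 | 0.0611 | 12.7% |
| 0.02 | 0 | 0 | 0.0800 | 0.0711 | 11.1% |
| 0.05 | 0 | 0 | 0.1100 | 0.1011 | 8.1% |
| 0.01 | 0.01 | 0 | 0.0700 | 0.0619 | 11.6% |
| 0.02 | 0.02 | 0.001 | 0.0890 | 0.0816 | 8.3% |
| 0.05 | 0.05 | 0.005 | 0.1550 | 0.1490 | 3.8% |

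Adding the step with a common coefficient leaves these savings unchanged. With tau = 0.02 and no cohort effects, an intercept-slope correlation of +0.5 or -0.5 moves the saving to 1% or 31%.

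**3. Step replaces linear time.** With no slopes or cohort effects: free 0.3 x (1 + 1/3) = 0.40; constrained 0.3/(3 - 9 x 0.7/3.1) = 0.31; saving 22.5%. It falls to 9.8% in the last setting of the table.

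**4. Linear and step terms both interact with arm.** In the seven settings of the table the saving is 0% on the linear term and 6-9% on the step.

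**5. Power for a linear effect of 0.30 at week 72** (0.10 per visit), half-versus-half contrast, t on 20 df:
- No random slopes: SE = sqrt(0.0600 x 2/108) = 0.0333, ratio 3.00, power about 81%. Constrained: ratio 3.25, about 87%.
- tau = 0.02: ratio 2.60, about 70%. Constrained: ratio 2.76, about 75%.

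A normal approximation gives values about 3 to 4 points higher.

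**6. A unit step in a linear fit.** With free intercepts the slope is (-0.5 + 0.5 + 1.5)/5 = 0.30 and the intercept 0.75 - 0.30 x 1.5 = 0.30. The constrained slope is (6 - 18 x 0.7/3.1)/5.871 = 0.33.

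**7. Type I error of the constrained linear test** (tau = 0). If a real u0 of 0.02, 0.05 or 0.10 is dropped and absorbed at person level: 5.3%, 5.8%, 6.4%. If it is kept and estimated (400,000 simulated null data sets per setting): 5.1%, 5.2%, 5.2%. With free intercepts: 5.0-5.1%.

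**The case against.** Free baseline terms are a standard, valid specification, and the strongest reply is that the gain may be nil where it is most wanted. The Statistical Analyses text speaks of adding a discontinuity, treats it as expected for Mind and perhaps unnecessary for Move, and says that time interactions with the factorial terms are included. One reading is that Mind has both a linear and a step interaction. The linear term then gains nothing. That stands, and it is why the saving cannot be quoted without the time coding.

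Other parts also stand. The size rests on variance components the SAP does not give. The planned model is slightly better calibrated, because the cohort intercept cancels from its slope contrast. Fixing the time coding can matter more than the constraint: for a step of 0.30 with no random slopes and free intercepts, a linear arm-by-time test has ratio 0.09/0.0333 = 2.70 (about 73% power on 20 df), while a step-by-arm test has 0.30/sqrt(0.40 x 2/108) = 3.49 (about 91%).

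The power figures depend on scaling too. If 0.30 is an unscaled difference of differences among four cells, the ratios in step 5 halve (3.00 to 1.50). Power without slopes is then only 32% to 37%, even by the normal approximation.

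None of this removes the point. Under the equations as printed, only linear time interacts with arm, and every such case tried shows some saving.

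**Conclusion.** The point holds as a cheap, optional improvement. At r = 0.7 the fall in variance is about 4-15% when only linear time interacts with arm (tau 0-0.05, u0 0-0.05, u1 0-0.005, no intercept-slope correlation), about 10-22% when the step replaces it, and 0% (linear) and 6-9% (step) when both interact. The variance components are treated as known.

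Three stronger readings are tempting, and the documents do not support them:
- A reader might infer that the planned tests are biased or ignore baseline. They do not: baseline enters the slope estimates, and free intercepts leave the arm-by-time tests unbiased with their nominal error rate. That statement covers this feature only; removing real cohort effects is a separate risk.
- A reader might infer that the SAP's 80% power does not count on this gain, or that it already does. Step 1 shows that either basis fits.
- A reader might take 0-31% as limits. It only spans cases tried: other assumed correlation structures gave up to 44%.

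Equality at baseline is in expectation, not in the observed means; that is all the constraint needs.

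**What to change.** Optional change to the Cluster-Level Model:

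1. Set time = 0 at baseline.
2. State, for Move, Mind and their interaction, whether linear time, the 0,1,1,1 term or both interact with arm.
3. Write `beta_00k = gamma_000 + gamma_004(ClinicSite) + u_00k`. Keep baseline as an outcome, with arm effects only in the time terms.
4. Keep the cohort random effects, above all `u_00k`, whatever their significance; the removal rule should not apply to this model.
5. Base any revised power statement on t with about 20 df, and say how the interaction effect is scaled.

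If free intercepts are kept, items 1 and 2 are still worth stating.

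The cost is text only: no extra participants or visits. There are two downsides. The constrained test depends more on retaining the cohort intercept variance (step 7). And a step-shaped effect fitted with linear time is summarised slightly differently (slope 0.33 rather than 0.30 per unit step).

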C3. Randomization. Participants will then be randomized to a condition and complete intervention orientation by the interventionist. Because the *Move* intervention is group-based, all participants will be cluster-randomized by clinic recruitment site and will return to the same site five times over 24 weeks for group meetings. At the 24-, 48-, and 72-week data collection appointments, participants will return to the site to complete appropriate measures, wear the ActiGraph for seven days, and return it as described above. The data collector will be naïve to the randomization condition. Beginning in week 27 of Year 1, 7 weeks are allocated to recruit and complete baseline data collection appointments with 10-11 patients from each of the 2 clinic recruitment sites (1-2 patients per site per week). Once all 10-11 participants have been recruited for a site, participants are randomized and told of their study condition (*Move*, *Mind*,

MindMoves, and usual care control) at their respective intervention orientations. Recruitment then begins for the next cohort of 10-11 participants at each site.

C4. Intervention Orientation. Intervention Orientation will occur following randomization during a separate orientation appointment conducted by the interventionist. The Intervention Orientation will occur at a location convenient to the participant. In the alternative intervention orientation protocol, all appointments will occur at the participants' homes, and contact will be minimized.

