**NCT04556305**

**01.26.2021**

## STATISTICAL DESIGN AND POWER

### Power Analysis

**Power Analysis.** Power was estimated using design effect methods to account for clustering of cases within randomized cohorts. Due to the group meeting component of *Move*, participants will be randomized into groups of 10-11 participants. Assuming 24 cohorts of 10-11 participants each (6 cohorts per cell in the 2x2 factorial design; Figure 3), a 15% attrition rate (a conservative estimate based on our previous results), and a correlation of 0.7 between assessments of memory performance (as measured by neurocognitive tests), we estimate 80% power to detect an interaction effect ( $d = 0.30$ ) for significance ( $p < 0.05$ ) with  $N = 254$  participants (216 after accounting for attrition). This is a reasonable minimal effect size for the interaction effect described in Aim 1. Although existing systematic reviews suggest an estimated effect size of  $d = 0.50$ , we estimate  $d = 0.40$  given our previous work as a more conservative estimate for the main effects of the *Move* and *Mind* interventions. Assuming an effect size of  $d = 0.40$ , our study design has > 90% power. Thus, 254 women with CVD will be recruited (63-64 in each cell).

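### The SAP allocates whole cohorts to treatment but drops the cohort random effects when they test non-significant, which makes the Move, Mind and interaction tests anti-conservative if change clusters within cohorts

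*SAP*

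**What the plan says.** **Allocation.** The SAP's Power Analysis section states that "Power was estimated using design effect methods to account for clustering of cases within randomized cohorts" and assumes 24 cohorts of 10–11, with "6 cohorts per cell in the 2x2 factorial design". Protocol 4.2.a, C3 (Randomization) says "all participants will be cluster-randomized by clinic recruitment site".

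**Model.** The SAP's Statistical Analyses section has observations "nested within participants, and participants nested within cohorts". In the Cluster-Level Model, Move, Mind and MindMoves appear only in the cohort-level equations, for level and for time slope, alongside clinic site.

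**Primary test.** Under Aim 1, "significant Move x Time, Mind x Time, and Move x Mind x Time effects will provide evidence of significant main effects", with the three-way term as evidence for the interaction. Aim 2 uses the same models.

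**Removal rule.** The Cluster-Level Model section puts cohort random effects in the initial models but considers "it is likely that the cluster-level random effects for the intercept" and time slope to be non-significant, and adds: "If non-significant, those random effects will be removed from the models". The SAP gives no ICC, no method for testing the variance components and no degrees-of-freedom method. It has no robust variance or sensitivity analysis that would bring the clustering back after removal.

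**The concern.** When whole cohorts receive a treatment, the treatment contrast is exposed to cohort-to-cohort variation. For the Aim 1 and Aim 2 time interactions, that variation is the cohort random slope. If it is removed while real, the tests use person-level error on about 211 degrees of freedom instead of cohort-level error on 19. Standard errors are then too small and the stated alpha of .05 is not held.

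A non-significant variance test would be reassuring only if the test could detect clustering of a size that matters. With 24 cohorts it cannot. The sample size allows for clustering through a design effect, yet the analysis is expected to proceed as if there were none.

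**Working it through.** **Inputs.** From the SAP's Power Analysis: 24 cohorts, 6 per cell; N = 254; 15% attrition; correlation 0.7; 80% power at d = 0.30; more than 90% at d = 0.40. From Data Management: alpha .05, taken as two-sided. Assumed, because not stated: the ICC of change, equal cohorts, and the variance test.

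**1. The plan's own figures.** 254 × 0.85 = 215.9, so 216 completers, or 216/24 = 9 per cohort. Each factorial contrast compares 108 with 108. The standard error is √(v × DE × 2/108), where v is the variance of the analysed quantity in units of the outcome variance and DE = 1 + (9 − 1) × ICC. Solving for the DE that gives exactly 80% power at d = 0.30:

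- Change score: v = 2(1 − 0.7) = 0.60; DE = 1.032; ICC = 0.032/8 = 0.004.
- Baseline-adjusted: v = 1 − 0.7² = 0.51; DE = 1.214; ICC = 0.214/8 = 0.027.

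Both take d = 0.30 as a 108 v 108 contrast at one follow-up. If d = 0.30 is the full difference of differences, power is only about 30–34% even at ICC 0, and no ICC reproduces 80%. The stated power can be matched but does not identify the ICC.

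**2. Degrees of freedom.** Cohort level: 24 − 4 cells − 1 site = 19. Within cohorts: 24 × (9 − 1) = 192. Pooled: 19 + 192 = 211.

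**3. Power of the test that decides removal.** The ratio MSB/MSW follows [1 + 9 × ICC/(1 − ICC)] × F(19, 192). Power of the 5% F test is 6% at ICC 0.004, 18% at 0.027, 34% at 0.05 and 80% only at about 0.126. A one-sided Wald test reaches 80% only at about 0.185.

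**4. Type I error under the rule.** Balanced nested model of person-level change, 4,000,000 simulated trials per setting: MSB ~ (σw² + 9σb²)χ²(19)/19 and MSW ~ σw²χ²(192)/192. If the cohort variance is significant, use MSB on 19 df; otherwise use the pooled mean square on 211 df. Ranges run from the F-test rule to the Wald rule.

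| ICC | All 24 cohorts cluster | Only the 12 Move-containing cohorts cluster |
|---|---|---|
| 0 | 4.8–5.0% | – |
| 0.004 | 5.1–5.3% | 4.9–5.2% |
| 0.01 | 5.5–5.9% | – |
| 0.027 | 6.5–7.4% | 5.7–6.2% |
| 0.05 | 7.2–9.0% | 6.4–7.2% |

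With equal clustering, the term is removed in 94–99% of trials at ICC 0.004 and 82–97% at 0.027. Always keeping it, on 19 df, gives 5.0% throughout. In the balanced design the three treatment contrasts are orthogonal, so the rates apply to each.

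**5. Power with the term kept.** Noncentral t on 19 df at the implied ICCs: 75.7% for d = 0.30 and 94.3% for d = 0.40, the same under both readings.

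**The case against.** **The inflation may be negligible.** The model treats baseline as a repeated outcome and gives each cell its own intercept, which is closer to the change-score reading (ICC 0.004, 5.1–5.3%) than to baseline adjustment. This is fair, but that reading uses one follow-up. Averaging three follow-ups gives v = (1 + 2 × 0.7)/3 + 1 − 2 × 0.7 = 0.4, DE = 0.6 × 1.032/0.4 = 1.548 and ICC = 0.548/8 ≈ 0.068, with type I error of about 7.3–9.9%. The implied ICCs are illustrations, not bounds.

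**Clustering is most plausible where there are group meetings.** Only Move and MindMoves hold them; Mind is home-based, and clinic site is already a fixed effect. This stands, and the right-hand column of the table may be the more natural case. Inflation there is smaller but does not vanish.

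**The upper end depends on an unnamed test.** Correct. A boundary-corrected likelihood-ratio test gives 6.6% at ICC 0.027, near the F-test end.

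**The unit of randomisation is worded loosely.** Protocol 4.2 speaks of participants being randomised, and C3 says "Once all 10-11 participants have been recruited for a site, participants are randomized and told of their study condition". However, six cohorts of 10–11 per cell match the planned 63–64 women per cell, and treatment enters only at cohort level. Cohort allocation is the reading on which the SAP is built.

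**The remedy also costs something.** It does: power falls, and unbounded variances with 24 cohorts can give inadmissible covariance estimates. The fix needs a fallback for that.

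**Conclusion.** The concern holds and should be fixed. The mechanism is certain: the rule conditions the primary error term on a test too weak to detect clustering of relevant size, and nothing later restores the clustering. The size is not certain. With no clustering there is no inflation. At the ICCs implied by two readings of the stated power it is about 5.1–7.4% with equal clustering, or 4.9–6.2% if only the Move-containing cohorts cluster. At ICC 0.05 it reaches 7.2–9.0% with equal clustering. These figures assume equal cohorts of nine and a simplified model of person-level change. They concern the cohort slope; removing only the random intercept matters much less for the time interactions.

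**What to change.** Replace the removal sentence in the Cluster-Level Model section with text such as: *The cohort-level random effects for intercept and time slope will be retained in all models regardless of statistical significance, with their variances estimated without a lower bound of zero. Move, Mind and interaction effects will be tested with Kenward-Roger degrees of freedom. If a cohort variance has to be set to zero, the tests will use the between-cohort degrees of freedom (24 cohorts minus the cluster-level parameters; 19 with clinic site).*

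In Power Analysis, state the assumed ICC and restate power on these degrees of freedom. State the unit of randomisation once, in the same terms in both documents.

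**Cost.** No study procedure changes. Power at d = 0.30 is about 76% against the stated 80%; at d = 0.40 it is about 94%, still above the stated 90%. The critical value rises from 1.97 to 2.09, so intervals are about 6% wider (2.09/1.97 = 1.06) even where cohort variance is near zero. If the variance is bounded at zero and 19 df are kept, the test is conservative: 3.0% at ICC 0 and 4.0% at 0.027.
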